11.3.2. Assigning Adverse Events to Study Year

The following rules will be used for allocating AEs to study year:

- Each AE will be reported in the year it started.
- AEs continuing for more than one treatment year will only be reported in the year they first occurred.
- If distinct episodes (start and stop date) of an AE are reported in multiple years, the AE will be reported once in each study year in which the unique event began.
- AEs with partial start and/stop dates will be assumed to have occurred on treatment unless there is evidence through comparison of partial dates to suggest otherwise.
- Where possible the non-missing information will be used to assign the AE to a study year, if the non-missing information is insufficient to assign the AE to a study year then the AE will be assigned to the earliest plausible study year.
- If the AE onset date is missing assume the start date was in Year 0-1. The event will be reported in Year 1 and "Any Time Post-Baseline."
- If the AE end date is missing assume the AE continued until the end of study. The AE will be reported in year of onset and "Any Time Post-Baseline."
- AEs that begin and end on the first day of treatment will count in the Year 0-1 period and for "Any Time Post-Baseline."

Table 15 Example of Assigning AEs to Study Years

Scenari o	Pre-Treatment	Year 0-1	Year 1-2	Year 2-3	Year 3-4	Year 4-5	After End of Treatment
Α	←						
В		←					
С		4					———
D	←		+				

NOTE: Arrow indicates the start and stop date of a single AE.

Scenari	Assignment of AE to Study Year Any Time Post-Baseline Year 0-1 Year 1-2 Year 2-3 Year 3-4 Year 4-									
0										
Α	No	No	No	No	No	No				
В	Yes	Yes	No	No	No	No				
С	Yes	Yes	No	No	No	No				
D	Yes	No	Yes	No	No	No				

11.4. Appendix 4: Data Display Standards & Handling Conventions

11.4.1. Study Treatment & Sub-group Display Descriptors

Treatment Group Descriptions								
Parent Study Parent Study Display Group [1]								
Belimumab 10 mg/kg IV	Belimumab							
Placebo IV	Placebo							
Belimumab 200 mg SC	Belimumab							
Placebo SC	Placebo							

NOTES:

[1] The "Belimumab" group will consist of those on 10 mg/kg IV and 200 mg SC during the parent study PRIOR to joining BEL114333. The "Placebo" group will consist of those on IV and SC during the parent study PRIOR to joining BEL114333.

11.4.2. Baseline Definition

Belimumab baseline is defined as the last available value prior to the time of initiation of belimumab treatment. See Figure 1.

- For subjects who were randomised to receive belimumab treatment in the parent study, 'baseline' is the last value prior to the first dose of belimumab received in the parent study.
 - For most assessments, this will be the assessment conducted at the baseline visit, but it may be the screening visit if the baseline assessment is missing, or if the assessment was only scheduled to be performed at screening.
 - If the baseline values originally derived for the parent study analyses are found to be calculated from data occurring post treatment, those values will be re-derived or set to missing.
- For subjects who were randomised to placebo in the parent study, 'baseline' is the last available value prior to the first open-label belimumab dose i.e. either in BEL112341 open-label extension or BEL114333. For most assessments, this will be the assessment at the parent study DB Week 52 visit. For some assessments, not available or missing at Week 52, baseline will be the last available value prior to belimumab start date, whether in the parent study (back to the DB Week 48 visit) or either in BEL112341 open-label extension or BEL114333.
- Baseline demographic characteristics not captured at the beginning of BEL112341 open-label extension or BEL114333, will be pulled from the baseline of the parent study.

11.4.2.1. Baseline SLE Disease Duration

• Baseline SLE Disease Duration in years is calculated as follows:

Date of First belimumab Treatment / Baseline Visit – (Date of SLE Diagnosis)+1 365.25

11.4.2.2. Total Number of ACR Criteria at Baseline

- ACR criteria were only collected at screening of the parent study, so all baseline values will be derived from parent study regardless of the randomized treatment group in the parent study.
- The total number of ACR criteria will be summed for a total possible score of 11.
- Subjects were required to have at least 4 to be eligible for the study.
- If sub-questions are present for a criterion, the sub-questions will be checked programmatically for the creation of the total score rather than the overall criterion score.

11.4.2.3. SLE Flares at Baseline

- Per the CRF page design, the assessment window for deriving categories at baseline of 'No flare', 'At least one flare', 'At least one severe flare' is the time interval between the last SLE assessment and 'baseline' (~4 weeks), defined as follows:
 - For subjects randomized to belimumab in the parent study, the time interval is from screening to baseline of the parent study.
 - For subjects randomized to placebo in the parent study BEL113750, the time interval is from Week 48 to Week 52 of the parent study.
 - o For subjects randomized to placebo in the parent study BEL112341, the time interval is Week 48 to Week 52 of the DB phase of BEL112341.

11.4.2.4. Derivations and Handling of Missing Baseline Data

Definition	Reporting Details
Change from Baseline	= Post-Dose Visit Value – Baseline
% Change from Baseline	= 100 x [(Post-Dose Visit Value – Baseline) / Baseline]

NOTES:

- Unless otherwise specified, the baseline definitions specified in Section 11.4.2 Baseline Definitions will be used for derivations for endpoints / parameters and indicated on summaries and listings.
- Unless otherwise stated, if baseline data is missing no derivation will be performed and will be set to missing.
- The baseline definition will be footnoted on all change from baseline displays.

11.4.3. **Reporting Process & Standards**

Reporting Process								
Software								
The currently support to the currently su	oported versions of SAS software 9.3 or higher will be used.							
Reporting Area	Reporting Area							
HARP Server	: US1SALX00259							
HARP Area	: arprod\gsk1550188\bel114333\final_01							
QC Spreadsheet	QC Spreadsheet : arprod\gsk1550188\bel114333\final_01\documents							
Note: \data_look_01	Note: \data_look_01 will be used for the run dry.							
Analysis Datasets								

- Analysis datasets will be created according to CDISC standards.
- For creation of ADaM datasets (ADCM/ADAE), the same version of dictionary datasets will be implemented for conversion from SI to SDTM.

Generation of RTF Files

RTF files will be generated for all tables in the final reporting delivery.

Reporting Standards

General

- The current GSK Integrated Data Standards Library (IDSL) will be applied for reporting, unless otherwise stated (IDSL Standards Location: https://spope.gsk.com/sites/IDSLLibrary/SitePages/Home.aspx)
 - 4.03 to 4.23: General Principles
 - 5.01 to 5.08: Principles Related to Data Listings
 - 6.01 to 6.11: Principles Related to Summary Tables
 - o 7.01 to 7.13: Principles Related to Graphics

Formats

- GSK IDSL Statistical Principles (5.03 & 6.06.3) for decimal places (DP's) will be adopted for reporting of data based on the raw data collected, unless otherwise stated.
- Numeric data will be reported at the precision collected on the eCRF.
- The reported precision from non eCRF sources will follow the IDSL statistical principles but may be adjusted to a clinically interpretable number of DP's.

Planned and Actual Time

- Reporting for tables, figures and formal statistical analyses:
 - Planned time relative to dosing will be used in figures, summaries, statistical analyses and calculation of any derived parameters, unless otherwise stated.
 - The impact of any major deviation from the planned assessment times and/or scheduled visit days on the analyses and interpretation of the results will be assessed as appropriate.
- Reporting for Data Listings:
 - Planned and actual time relative to study drug dosing will be shown in listings (Refer to IDSL Statistical Principle 5.05.1).
 - Unscheduled or unplanned readings will be presented within the subject's listings.

Unscheduled Visits

Reporting Standards

- Unscheduled visits will be included in summary tables and/or figures in the 'Any Time Post baseline' time interval. Otherwise, unscheduled visits will not be displayed in by visit summaries or figures.
- All unscheduled visits will be included in listings.

Descriptive Summary Statistics							
Continuous Data	Refer to IDSL Statistical Principle 6.06.1						
Categorical Data N, n, frequency, %							
Graphical Displays							
Refer to IDSL Statistical Principals 7.01 to 7.13.							

11.5. Appendix 5: Derived and Transformed Data

11.5.1. **General**

Subject Identifier, Breaks in Treatment and Date of Last Visit

Subject Identifier

- Subjects enrolled in BEL114333 from the parent study BEL113750 continued to use the same subject identifier as assigned in the parent study. Note: the site identifiers used in the parent study BEL113750 were changed in BEL114333 in order to retain the same subject identifier.
- Subjects enrolled in BEL114333 from the parent study BEL112341 were assigned subject identifiers ranging from 9001 to 9030.

Dose Interruption

- The first dose in the study BEL114333 must be given 4 weeks (minimum of 2 weeks, maximum of 8 weeks) after the last IV dose for subjects enrolled from the parent study BEL113750.
- For subjects from the SC parent study BEL112341, the first IV dose in study BEL114333 is targeted for 1 week (+1 week window) after the last dose of SC belimumab (scheduled for Week 23 in the OL extension part of BEL112341).

Note: For the purposes of reporting, dose interruptions will be ignored and exposure will be treated as continuous.

Date of Last Visit

- Last visit date (in BEL114333) will be defined as the exit visit date, where available.
- For subjects who do not have an open-label exit visit date, and only have a follow up date, the following will be used to derive a last visit date in order of priority:
 - 1. Death Date if non-missing and prior to Disposition Date
 - 2. Disposition Date, if non-missing
 - 3. If last non-follow up visit is after last dose of belimumab, use the minimum of a) the last non-follow up visit date, or b) the last dose date + 28 days.
 - 4. If the last non-follow up visit is prior to the date of last dose, use the last dose date.
- Time to withdrawal (in days) will be calculated for each subject as
 - O Time to Withdrawal = Date of Last Visit First Dose Date of Belimumab + 1

Date of Last Contact

 Final contact (in BEL114333) will be defined as the latest visit, as appropriate, up to the 6 month FU visit (post-last dose of belimumab).

Multiple Measurements at One Time Point

 Subjects having both High and Low values for Normal Ranges at any post-baseline visits for safety parameters will be counted in both the High and Low categories of "Any visit postbaseline" row of related summary tables. This will also be applicable to relevant Potential Clinical Importance summary tables.

Study Day

- Calculated as the number of days from first dose date of belimumab treatment:
 - Ref Date = Missing → Study Day = Missing
 - Ref Date < First Dose Date → Study Day = Ref Date First Dose Date
 - Ref Data ≥ First Dose Date

 → Study Day = Ref Date (First Dose Date) + 1

11.5.2. Study Population

Demographics

Age

- Full date of birth and age were collected at screening of the parent study, and will be available in the data transfer.
- Analysis age in years will be derived from the full date of birth and the first dose date of belimumab treatment, and will be calculated in SAS as:

INTCK ('YEAR', date of birth, first dose date, 'C')

• Birth date will be presented in listings as 'YYYY'.

Body Mass Index (BMI)

• BMI (kg/m²) = weight (kg) / height (m)² will be derived from height at screening visit of the parent study, and weight measured at the belimumab baseline.

11.5.3. Safety

Adverse Events, Laboratory, SLE Medication, Average Daily Steroid Dose

Adverse Events of Special Interest (AESI)

 AESI have already been identified by the Safety Review Team (SRT) (via an enhanced MedDRA dataset) and any event specific updates will be applied via an adjudication spreadsheet.

Laboratory Parameters

For laboratory values that are above or below the lower limit of quantification, having only
character values starting with "<" or ">", numeric values will be derived using the following rules,
where LRESSI in the character result in standard units, and LNRES is the numeric version of
the result:

```
If LRESSI = '> x' then LNRES = x + 1, where x is an integer \ge 1.

If LRESSI = '> x.y' then LNRES = x.y + 0.1, where x, y are integers.

If LRESSI = '> x.yz' then LNRES = x.yz + 0.01, where x, y, z are integers.
```

Laboratory Parameters

```
If LRESSI = '< x' then LNRES = x - 1, where x is an integer \geq1.

If LRESSI = '< x.y' then LNRES = x.y - 0.1, where x, y are integers.

If LRESSI = '< x.yz' then LNRES = x.yz - 0.01, where x, y, z are integers.

etc
```

SLE Medication Categories

 Concomitant medications will be reviewed and may be assigned to one of five categories based on their GSK Drug Dictionary preferred terms (using the current version of GSK Drug at the time of reporting) for summarisation throughout the course of the study: corticosteroid, anti-malarial, immunosuppressant, NSAID and Aspirin, and defined as:

Medication category	Definition
Corticosteroid	ATC code starts with "H02" and route of administration is intravenous, intramuscular, subcutaneous, intradermal, intraarticular or oral.
Anti-malarial	Preferred term includes QUINACRINE, QUININE, HYDROXYCHLOROQUINE, MEPACRINE or CHLOROQUINE.
	Meds with the following routes of administration will be excluded : topical, vaginal, conjunctival, intranasal, inhaled, intra-ocular, intratracheal, epidural, intra-articular or other.
Immunosuppressant	ATC code starts with "L04A" or preferred term contains CYCLOPHOSPHAMIDE, MERCATOPURINE or METOTREXATE.
	Meds with the following routes of administration will be excluded : topical or conjunctival.
	ATC code of "M01A".
NSAID	Meds with the following routes of administration will be excluded : topical or conjunctival.
	Coded term contains ACETYLSALICYCLIC ACID or ACETYLSALICYLATE LYSINE.
Aspirin	Meds with the following routes of administration will be excluded : topical or conjunctival.

Average Daily Steroid Dose

- Concomitant medications, including corticosteroids, were collected in both the parent studies and BEL114333. To determine average daily dose and for analysis of steroid use, all steroid dosages are converted to a prednisone equivalent dosage in milligrams.
- The average daily prednisone dose considers all steroids taken systemically intravenously (IV), intramuscularly (IM), SC, intradermally, and orally for both SLE and non-SLE reasons.
- At baseline, the average daily prednisone dose is the sum of all prednisone doses over 7 consecutive days up to, but not including Day 0, divided by 7.
- While on treatment, the average daily prednisone dose is the sum of all prednisone doses over 7 consecutive days, including the day of interest, divided by 7, unless otherwise specified.
- This average dose will be categorised as 0, >0 to ≤7.5, >7.5 to ≤40, and >40 mg/day. The
 average daily prednisone dose will be calculated for weeks 24 and 48 for each year.

Prednisone Equivalent Daily Dose Conversions

- At data base lock, all preferred terms identified with an ATC code beginning with 'H02' will be
 reviewed to ensure a conversion factor exists for all terms with a systemic or intra-articular route
 of administration.
- Similarly, all routes of administration for preferred terms
- Reported dose of systemic steroid is converted to prednisone equivalent dose using a conversion factor for each medication (refer to online calculator http://www.globalrph.com/corticocalc.htm).
 - Prednisone equivalent dose (mg/day) =
 Collected dose (mg) x Conversion Factor x Frequency Factor

[figure not shown]
Preferred Term	Conversion Factor for Prednisone-Equivalent Dose (mg)					
BETAMETHASONE	8.333					
BETAMETHASONE DIPROPIONATE	8.333					
BETAMETHASONE SODIUM PHOSPHATE	8.333					
BUDESONIDE	No conversion applied – nasal spray taken by 1 subject in BEL113750					
CELESTONA BIFAS	7.5					
CORTISONE	0.2					
CORTISONE ACETATE	0.2					
DEFLAZACORT	5/6					
DEPO-MEDROL MED LIDOKAIN	1.25					
DEXAMETHASONE	6.667					
DEXAMETHASONE ACETATE	6.667					
DEXAMETHASONE SODIUM PHOSPHATE	6.667					
FLUOCORTOLONE	3					
HYDROCORTISONE	0.25					
HYDROCORTISONE ACETATE	0.25					
HYDROCORTISONE SODIUM SUCCINATE	0.25					
MEPREDNISONE	1.25					

[figure not shown]
METHYLPREDNISOLONE	1.25
METHYLPREDNISOLONE ACETATE	1.25
METHYLPREDNISOLONE SODIUM SUCCINATE	1.25
PARAMETHASONE	2.5
PREDNISOLONE	1
PREDNISOLONE ACETATE	No conversion applied - conjunctival
PREDNISOLONE SODIUM PHOSPHATE	1
PREDNISOLONE SODIUM SUCCINATE	1
PREDNISONE	1
PREDNISONE ACETATE	1
TRIAMCINOLONE	1.25
TRIAMCINOLONE ACETATE	1.25
TRIAMCINOLONE ACETONIDE	1.25
Frequency Factors	1.20
Frequency	Factor
BID	2
BIW	2/7
OAM	1/30
ONCE	1
PRN	null
Q2H	12
Q2W	1/14
Q3H	8
Q3MO	1/84
Q3W	1/21
Q4H	6
Q4W	1/28
Q6H	4
Q8H	3
QAM	1
QD	1
QH	24
QHS	1
QID	4
QM	1/30
QOD	1/2
QPM	1
QW	1/7
QWK	1/7
TID	3
TIW	3/7
1 TIME PER WEEK	1/7
2 TIMES PER WEEK	2/7
3 TIMES PER WEEK	3/7

EVERY 2 WEEKS	1/14
EVERY 4 WEEKS	1/28
EVERY WEEK	1/7
UNKNOWN	null

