Patients with SLE have about a 3-fold greater risk of mortality than the general population. Approximately 70% of SLE patients survive 20 years from time of diagnosis [Houssiau, 2004]. Standard therapies for SLE include corticosteroids (the mainstay of therapy), anti-malarial agents (e.g., hydroxychloroquine), non-steroidal anti-inflammatory drugs (NSAIDs), cytotoxic agents like cyclophosphamide, and immunosuppressive/immunomodulatory agents (e.g., azathioprine, cyclosporine, mycophenolate mofetil (MMF), methotrexate, leflunomide, thalidomide, 6-mercaptopurine) [Petri, 2001; Reveille, 2001; Ginzler, 2005; Houssiau, 2004; Ruiz-Irastorza, 2001; Wallace, 2002; Brocard, 2005; Chatham, 2001]. Although active lupus nephritis and CNS vasculitis can usually be controlled with several courses of high dose steroids and cyclophosphamide over a 1 to 2 year period, there tends to be progressive relapsing of disease over time [Petri, 2001; Houssiau, 2002; Illei, 2001; Ruiz-Irastorza, 2001]. These therapies can be associated with significant toxicity. Long-term use of high-dose corticosteroids can cause significant morbidity including osteoporosis, osteonecrosis, metabolic disorders (including exacerbation of diabetes), increased infection risk, edema, weight gain and hyperlipidemia [Chatham, 2001]. Cytotoxic agents like cyclophosphamide are immunosuppressive, resulting in increased risk of serious infections and certain cancers.

The prevalence of SLE in Hong Kong & mainland China was found to range from 58.8/100,000 to 73.3/100,000 in two studies [Mok, 2003; Xiang, 2009]. When compared with US SLE prevalence estimates of 100.0/100,000 [Naleway, 2005; Chakravarty, 2007], SLE disease burden does not appear to be higher in China. Conversely, SLE prevalence in the EU 5 regions (UK, Germany, France, Spain, and Italy) was estimated at 43.0/100,000 [Govoni, 2006; Lopez, 2003; Nightingale, 2006] which is lower than in China. Regarding disease activity, Boers [Boers, 2006] reported more severe SLE among Asian patients admitted to a medical centre in Australia, with Southeastern Asian/Chinese

patients having a median Systemic Lupus Erythematosus Disease Activity Index (SLEDAI) of 13 at first admission compared to a median SLEDAI of 8 among Caucasians.

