Allowable SLE Medication Usage	Counts (%) by class for: Steroid only, Immunosuppressant only, Anti-malarial only, Steroid and Immunosuppressant only, Steroid and Anti-malarial only, Immunosuppressant and Anti-malarial only, Steroid, Immunosuppressant and Anti-malarial only.
	Counts (%) for preferred term within drug class (Steroid, Other Immunosuppressant/immunomodulatory Agents, Anti-malarial, NSAIDs and Aspirin).
Average daily prednisone dose (mg/day)	Summary statistics.
at baseline	• Counts (%) for dose categories: 0, >0 to ≤ 7.5, >7.5 to ≤ 40 and >40 mg/day

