7.1.2. SLE Medications

- Corticosteroids, anti-malarials, other immunosuppressive/immunomodulatory agents, NSAIDs and Aspirin will be categorized based on the coded preferred terms, and summarized by yearly interval using frequencies (%).
- For summaries, all corticosteroids taken during belimumab treatment are converted to a prednisone equivalent dose (mg/day). This then can be used for the derivation of average daily dose, see Appendix 5: Derived and Transformed Data.
- Use of prednisone or other corticosteroids during the study were collected as a running log with other concomitant medications, and will be summarized using dose level categories: 0, > 0 to ≤ 7.5 or > 7.5 to ≤ 40 , and > 40 mg/day.

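### Three misspelled search strings in the SLE medication definitions could drop aspirin, methotrexate and mercaptopurine records from the descriptive medication tables if programmed literally

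*SAP*

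**What the plan says.** SAP 7.1.2 states that "NSAIDs and Aspirin will be categorized based on the coded preferred terms". It says the same of corticosteroids, anti-malarials and other immunosuppressive agents, and the results are summarised by year interval. SAP 11.5.3, under SLE Medication Categories, gives the rules and introduces them with this sentence: "Concomitant medications will be reviewed and may be assigned to one of five categories based on their GSK Drug Dictionary preferred terms". Two of the five definitions matter here.

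- **Immunosuppressant:** an ATC code beginning L04A, or "preferred term contains CYCLOPHOSPHAMIDE, MERCATOPURINE or METOTREXATE". Topical and conjunctival routes are excluded.
- **Aspirin:** "Coded term contains ACETYLSALICYCLIC ACID or ACETYLSALICYLATE LYSINE". The same routes are excluded, and no ATC code is offered as an alternative.

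Protocol 1.1 lists the standard therapies as "azathioprine, cyclosporine, mycophenolate mofetil (MMF), methotrexate, leflunomide, thalidomide, 6-mercaptopurine".

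The classes feed two tables: Table 1.26 (allowable SLE medication at baseline) and Table 2.3 (SLE medication by year interval). For baseline, SAP 6.2.1.1 (Table 6) plans single-class and combination rows built from steroid, immunosuppressant and anti-malarial use. It also plans "Counts (%) for preferred term within drug class", with aspirin among the classes.

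**The concern.** These strings are classification rules, not background prose, and a substring test tolerates no spelling error. METOTREXATE is not contained in METHOTREXATE, MERCATOPURINE is not contained in MERCAPTOPURINE, and ACETYLSALICYCLIC ACID is not contained in ACETYLSALICYLIC ACID. A programmer who follows the text exactly would get no match on the normally spelled drug names.

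At stake is the description of background therapy. Protocol 5.3.1 gives investigators more latitude to change it than in the parent study, and SAP 2.1 drops the duration-of-response endpoint because of that freedom. Readers will therefore use the SLE medication tables as context for the long-term results.

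**Working it through.** No sample size, power or other figure in the plan bears on this point, so there is nothing to reproduce. The check is a literal substring test. A drug name is classified if any string in its class definition occurs inside it.

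**Inputs.** The strings come from SAP 11.5.3. The spellings methotrexate and 6-mercaptopurine come from Protocol 1.1. The documents do not spell out acetylsalicylic acid correctly anywhere relevant, so the normal spelling is assumed. The SAP's own second aspirin string supports it: that string uses the stem ACETYLSALICYL-, while the first uses ACETYLSALICYC-.

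**Step 1: distance between each string and the normal spelling.**

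| SAP string | Normal spelling | Letter edits |
|---|---|---|
| CYCLOPHOSPHAMIDE | CYCLOPHOSPHAMIDE | 0 |
| MERCATOPURINE | MERCAPTOPURINE | 1 (P dropped) |
| METOTREXATE | METHOTREXATE | 1 (H dropped) |
| ACETYLSALICYCLIC ACID | ACETYLSALICYLIC ACID | 1 (C added) |
| ACETYLSALICYLATE LYSINE | ACETYLSALICYLATE LYSINE | 0 |

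Three of the five strings are wrong by one letter.

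**Step 2: does the drug name match its class strings?**

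| Drug name tested | As written | Corrected |
|---|---|---|
| Cyclophosphamide | yes | yes |
| Mercaptopurine; 6-mercaptopurine | no | yes |
| Methotrexate; methotrexate sodium | no | yes |
| Acetylsalicylic acid, alone or in combination | no | yes |
| Acetylsalicylate lysine | yes | yes |

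**Step 3: add the ATC route.**

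- *Immunosuppressants.* The L04A condition is joined to the strings by OR, so a methotrexate or mercaptopurine record is lost only if it has no L04A code. The loss is every such record without L04A. The documents do not give the ATC codes assigned to these drugs, so it lies anywhere from none of these records to all of them.
- *Aspirin.* There is no ATC condition, so every acetylsalicylic acid record is lost from the class and only acetylsalicylate lysine remains. The documents do not show whether such records carry M01A and would be counted as NSAIDs instead.

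**Step 4: effect on the tables.** Take *k* subjects whose baseline therapy is a steroid plus methotrexate, with no L04A code on the record and no other immunosuppressant or anti-malarial. Each moves from the steroid-plus-immunosuppressant row to the steroid-only row. The first is then too low by *k* and the second too high by *k*. Aspirin does not enter these rows; its loss shows only in its own class counts.

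**The case against.** The strongest answer is that the SAP does not describe an unattended string match. Its opening sentence says medications will be reviewed and may be assigned, which leaves room for someone to notice that methotrexate or aspirin is unclassified. No program is shown, and the working code may already use correct spellings. This stands, and it is why no effect on results can be claimed. It does not remove the defect: the same sentence leads into definitions built on the wrong strings, and no check of terms left in no class is written.

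Four further points stand in part.

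- The dictionary is not in the documents, and some coded terms in the steroid conversion table are not standard English names. Normal spelling for these three drugs is likely, but it is an assumption.
- L04A may capture every methotrexate and mercaptopurine record, and then the immunosuppressant class loses nothing. A reader might infer that the strings were added specifically for drugs outside L04A. The SAP does not state their purpose, and the point does not need it.
- The drugs remain visible elsewhere. Table 2.2 tabulates concomitant medications by ATC level 4 and preferred term, and Listing 14 lists them. An aspirin class without acetylsalicylic acid would also look odd in Table 1.26.
- A text-extraction fault cannot be wholly excluded, but one dropped P, one dropped H and one added C in three separate words look like typing errors.

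A reader might also think that the steroid review in SAP 11.5.3 is a model for the missing check. It is not: it confirms that terms already found by an H02 code have a conversion factor, and it does not search for unclassified drugs.

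**Conclusion.** The written specification is wrong; the consequence is minor and conditional. If the rules are programmed literally and the GSK Drug Dictionary uses normal spellings, the Aspirin class holds only acetylsalicylate lysine, and methotrexate or mercaptopurine records without an L04A code are missed. Tables 1.26 and 2.3 could then understate aspirin and immunosuppressant use, and the baseline combination rows could misplace subjects because of the missed immunosuppressants. The number affected cannot be calculated from the documents.

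Two stronger readings are tempting and not supported. The first is that the tables will understate use: this ignores the planned review and the L04A route. The second is that efficacy results are at risk. The SLE medication classes are not covariates or subgroups (SAP 11.8), there is no hypothesis testing (SAP 2.4), and the prednisone endpoints rest on H02 codes and conversion factors.

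**What to change.** In SAP 11.5.3, change the three strings to MERCAPTOPURINE, METHOTREXATE and ACETYLSALICYLIC ACID. Add one sentence to the medication review already described there: before database freeze, list all preferred terms that fall in none of the five classes and have that list checked. The cost is three corrected words and one short listing. No data, endpoint or planned display changes.
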